#### 6.16.1.4. Time to SARS-CoV-2 Clearance

See Section 6.16.1.3 for more details on the definition of viral clearance and date of viral clearance.

Time to SARS-CoV-2 clearance is defined (in days) as:

*(Date of first negative SARS-CoV-2 RT-PCR test – Date of first positive SARS-CoV-2 RT-PCR test + 1)*

Only patients who have at baseline or later develop SARS-CoV-2 infection will be included in the analysis. If a patient has not experienced SARS-CoV-2 clearance by completion or early discontinuation of the evaluation period, the patient will be censored at the date of their last visit during the evaluation period.

Time to SARS-CoV-2 clearance will be evaluated during the study evaluation period only and will be summarized by treatment group, and listed for the Prevention and Treatment populations. Cox proportional hazard methodology will be used.

Time to SARS-CoV-2 clearance will be presented graphically.

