1.3. Schedule of Activities (SoA)

Screening procedures may be conducted over more than 1 day, as long as all activities are completed within the allowed interval tolerance. Screening and Day 1 procedures may occur on the same day.

Participants who test positive for SARS-CoV-2 during the Evaluation Period may have their scheduled visit(s) conducted as a remote health assessment. Refer to the study day and visit type table in Section 4.1.2 for additional clarification.

Early Termination Visits are conducted when the participant is withdrawn from the study prior to the post-evaluation follow-up.

1.3.1. Part 1 and Prevention Cohort of Part 2

Procedures	Screening	Evaluation Period										ETV	Post-Evaluation Follow-Up			Comments
		1	2-7	8	15	22	29	36	43	50	57		85	141	169	
Study Day	Max 7-day window	1	2-7	8	15	22	29	36	43	50	57		85	141	169	
Visit window (\pm number of days)	--	--	--	2	2	2	2	2	2	2	2		7	7	7	
Randomization		X														
Administer study intervention (IV infusion)		X														
Informed Consent	X															
Inclusion and exclusion criteria review	X															
Demographics	X															Including age, gender, race, ethnicity
Preexisting conditions and medical history	X															Obtained from interview or available information. For participants with symptoms suggestive of COVID-19, obtain timing of onset of symptoms

Procedures	Screening	Evaluation Period										ETV	Post-Evaluation Follow-Up			Comments
Study Day	Max 7-day window	1	2-7	8	15	22	29	36	43	50	57		85	141	169	
Visit window (\pm number of days)	--	--	--	2	2	2	2	2	2	2	2		7	7	7	
Prior treatments of special interest	X															Within the last 2 weeks: NSAIDs, antivirals, antibiotics, anti-malarials, corticosteroids, immunomodulators, or other investigational treatments. At any time: SARS-CoV-2 vaccine
Tobacco use	X															Never/ former/ current use
Concomitant medications	X	X	X	X	X	X	X	X	X	X	X	X	X	X		
Adverse events (AEs)	X	X	X	X	X	X	X	X	X	X	X	X	X	X	X	Any events that occur after signing the informed consent are considered AEs as defined in Section 10.3, Appendix 3.
Physical examination	X															
Symptom-directed physical exam		X										X	X	X		As indicated based on participant status and standard of care.
Height	X															
Weight	X															

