Vital signs	X	Daily										X	X	X		Documentation of hospital-based exam is acceptable. Includes: body temperature, pulse rate, BP, SpO ₂ , respiratory rate, FiO ₂ if known, and method of delivery, if applicable. Record while participant is at rest.

Procedures	Screening	Evaluation Period										ETV	Post-Evaluation Follow-Up			Comments
Study Day	Max 7-day window	1	2-7	8	15	22	29	36	43	50	57		85	141	169	
Visit window (\pm number of days)	--	--	--	2	2	2	2	2	2	2	2		7	7	7	
Hospitalization events		Daily										X	X	X		Record if the following events occur: 
Emergency room visitshospitalizedICU admittance,Extended care facility admittance,and discharge for any of the above
Clinical status and concomitant procedures of special interest in hospitalized participants		Daily										X	X	X		Documentation from hospital records is acceptable. Includes: consciousness status (ACVPU), limitation on activities due to COVID-19, and requirements for 
Ongoing hospital medical careSupplemental oxygennon-invasive ventilation or a high flow oxygen devicemechanical ventilationextracorporeal membrane oxygenation, oradditional organ support (e.g. pressors, renal replacement)
Clinical symptoms and interventions of interest		Daily										X	X			See Table 1 for clinical symptoms and interventions of interest.

Procedures	Screening	Evaluation Period										ETV	Post-Evaluation Follow-Up			Comments
Study Day	Max 7-day window	1	2-7	8	15	22	29	36	43	50	57		85	141	169	
Visit window (\pm number of days)	--	--	--	2	2	2	2	2	2	2	2		7	7	7	
Symptoms Questionnaire	X	Daily										X	X		See Section 8.1.2.	
SARS-CoV-2 POC Test (Nasal Swab)	X														Applies to participants in Part 2 only. Result must be determined prior to collecting swabs for PCR test.	
SARS-CoV-2 Serology		X				X			X	X	X	X	X	X	Day 1: pre-dose. assessed at a central laboratory	
SARS-CoV-2 nasopharyngeal swab (for PCR test) taken from both nostrils		X													Day 1: pre-dose. assessed at a central laboratory	
SARS-CoV-2 nasal swab (for PCR test) taken from both nostrils		X		X	X	X	X	X	X	X	X	X	X		Day 1: pre-dose. assessed at a central laboratory No samples needed if participant is hospitalized.*	

Procedures	Screening	Evaluation Period										ETV	Post-Evaluation Follow-Up			Comments
Study Day	Max 7-day window	1	2-7	8	15	22	29	36	43	50	57		85	141	169	
Visit window (\pm number of days)	--	--	--	2	2	2	2	2	2	2	2		7	7	7	

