The maximum total duration of study participation for each participant of the treatment group is 12 weeks. See the SOA for the treatment group in Section 1.3.2.

This table describes the visit types for the prevention population for this study.

Study Day	Activity	Visit Type
0,1	Follow SoA	Onsite
8, 15, 22, 29, 36, 43, 50, 57	Follow SoA Vital signs*	Onsite or Home (Virtual [record collection] if hospitalized)

Daily 2 - 57	Vital signs and symptoms questionnaire daily* Vital signs, clinical status, and concomitant procedures for hospitalized participants.	Onsite or Home (Virtual [record collection] if hospitalized)
ETV and follow-up (85, 141, 169)	Follow SoA	Onsite or Home

*Collected via direct data capture for onsite or home visits only.

This table describes the visit types for the treatment population for this study.

Study Day	Activity	Visit Type
0, 1	Follow SoA	Onsite
8, 29	Follow SoA Vital signs*	Onsite or Home (Virtual [record collection] if hospitalized)
Daily 2-29	Vital signs, clinical status, and concomitant procedures for hospitalized participants.	Virtual (record collection) if hospitalized
ETV and follow-up (85)	Follow SoA	Onsite or Home

*Collected via direct data capture for onsite or home visits only.

Hospitalization

If a participant is hospitalized, efforts will be made to retrieve hospital records and report procedures and assessments according to the SoA, as feasible.

Definitions for COVID-19 Severity

This table gives the definitions for COVID-19 severity of illness for those participants who are SARS-CoV-2 positive as determined by standard RT-PCR assay or equivalent test.

Table 1 Definitions for COVID-19 Severity

Severity	Description
Mild	Mild symptoms that could include: 
 fever, cough, sore throat, malaise, headache, muscle pain, gastrointestinal symptoms, without shortness of breath or dyspnea AND No clinical signs indicative of Moderate, Severe, or Critical Severity
Moderate	Symptoms of moderate illness with COVID-19, which could include any symptom of mild illness or shortness of breath with exertion AND Clinical signs suggestive of moderate illness with COVID-19, such as: 
 respiratory rate \geq 20 breaths per minute,

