#### 6.16.1.3. SARS-CoV-2 Clearance

For qualitative determination of viral clearance, the lab determination of “positive”/“negative” will be used. SARS-CoV-2 clearance (yes/no) is defined as a single negative RT-PCR test for the SARS-CoV-2 virus. The date of viral clearance is defined as the date of the first occurrence of a negative test.

The proportion of patients that achieve SARS-CoV-2 clearance within 1, 2, or 3 weeks of becoming SARS-CoV-2 positive will be summarized by treatment group in frequency tables and listed for the Prevention populations and the Part 1 Treatment population. Similar summaries will be made for the proportion of patients in the Part 2 Treatment and Part 3 treatment populations that achieve SARS-CoV-2 clearance within 8 and 29 days of becoming SARS-CoV-2 positive.

In addition, the number of patients that achieve SARS-CoV-2 clearance within 1, 2, or 3 weeks (or, for the Part 2 Treatment and Part 3 treatment populations, within 8 and 29 days) of becoming SARS-CoV-2 positive will be analyzed using logistic regression to compare treatment groups, if there are sufficient data available. Missing data will be imputed using the NRI method as described in Section 6.3.3. This comparison will be made on the Prevention and Treatment populations.

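### Time to SARS-CoV-2 clearance censors uncleared participants at their last visit, which can fall after their last RT-PCR, so untested days count as observed non-clearance (minor; exploratory endpoint)

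*SAP*

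**What the plan says.** **Event.** SAP 6.16.1.3: "SARS-CoV-2 clearance (yes/no) is defined as a single negative RT-PCR test for the SARS-CoV-2 virus". SAP 6.16.1.4 runs the clock from the first positive RT-PCR to the "Date of first negative SARS-CoV-2 RT-PCR test", plus one day.

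**Censoring.** SAP 6.16.1.4 says that, for anyone yet to have "experienced SARS-CoV-2 clearance by completion or early discontinuation of the evaluation period, the patient will be censored at the date of their last visit". It does not require that a swab was taken at that visit.

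**Model and scope.** "Cox proportional hazard methodology will be used", with a plot, in the Prevention and Treatment populations.

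**Swabs.** The RT-PCR swab rows in both schedules (Protocol 1.3.1 and 1.3.2) carry the note "No samples needed if participant is hospitalized". The footnote to each table adds two things: results from the hospital's own laboratory are not entered on the case report form, and the normal schedule resumes on discharge.

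**Visits.** The visit-type tables in Protocol 4.1.2 keep scheduled visits going during a hospital stay: "Onsite or Home (Virtual [record collection] if hospitalized". Protocol 1.3 also says that participants who turn positive "may have their scheduled visit(s) conducted as a remote health assessment".

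**What is absent.** No section moves the clearance censoring date to the last RT-PCR or names an interval-censored analysis. SAP 6.3.1, which does refer to the last available RT-PCR, covers missing infection status for the primary and key secondary endpoints, not clearance.

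**The concern.** Clearance status is known only on days with an RT-PCR result. Right-censoring at a later date tells the Cox model that the participant was under observation and still positive up to that date. When the last visit was a record-collection visit in hospital, nobody tested, and the statement has no data behind it.

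The gap need not fall equally on the arms. The schedules waive swabs only for hospitalised participants, and hospitalisation is an outcome that the drug is meant to reduce. If infected placebo participants are hospitalised more often than infected active participants, placebo collects more untested time at risk. The hazard ratio for clearance (above 1 means faster clearance on active drug) then rises even if clearance is identical in both arms.

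**Working it through.** **1. A figure to reproduce.** There is none. The documents give no event count, hazard ratio or power for time to clearance.

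**2. Who is affected.**

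- A participant who tests negative at any swab in the Evaluation Period has the event on that date. The censoring rule does not apply.
- A participant who never tests negative but is swabbed at the last visit has the same censoring date under either rule.
- The rules differ only for a participant who never tests negative and whose last visit had no swab. Examples are someone still in hospital at the end of the Evaluation Period, or withdrawn after admission.

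**3. Illustration on the weekly schedule.** First positive on Day 29, still positive on Day 36, then admitted and still in hospital on Day 57.

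- Last visit: 57 − 29 + 1 = 29 days.
- Last RT-PCR: 36 − 29 + 1 = 8 days.
- Untested time counted as non-clearance: 29 − 8 = 21 days.

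**4. Size by simulation.** Cox model (Breslow ties), 150,000 infected participants per scenario, same underlying clearance in both arms. All clinical inputs are assumptions because the documents give none: median clearance 14 days; admission 1 to 10 days after the first positive; mean stay 7 or 14 days; hospitalised shares of infected participants (placebo vs active) of 10% vs 10%, 10% vs 3%, 20% vs 5% and 30% vs 10%; and 0, 30% or 100% of the hospitalised never swabbed again. Some runs also slowed clearance in hospitalised participants by a factor of 1.5. In those runs the arms can truly differ, so only the gap between the two rules is informative.

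Hazard ratios for 20% vs 5% hospitalised, mean stay 14 days, no slower clearance in hospital (true value 1):

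| Population, weekly swabs | Hospitalised never re-swabbed | Last visit | Last RT-PCR | Due to the rule |
|---|---|---|---|---|
| Prevention | 0% | 1.09 | 1.04 | 0.05 |
| Prevention | 30% | 1.14 | 1.02 | 0.12 |
| Prevention | 100% | 1.29 | 1.00 | 0.29 |
| Part 1 Treatment | 0% | 1.076 | 1.059 | 0.017 |
| Part 1 Treatment | 30% | 1.178 | 1.049 | 0.129 |
| Part 1 Treatment | 100% | 1.386 | 0.999 | 0.387 |

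Over all scenarios with unequal shares, pooled over schedules including Days 1/8/29:

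| Hospitalised never re-swabbed | Due to the rule | Infected participants whose time changes |
|---|---|---|
| 0% | about 0 to 0.06 | 0–5% |
| 30% | about 0.03 to 0.16 | 2–9% |
| 100% | about 0.08 to 0.5 | 5–19% |

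With 10% vs 10% hospitalised, both rules gave about 1.00.

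**5. What remains after re-censoring.** The excess over 1.00 in the last-RT-PCR column comes from late detection: someone who clears in hospital is found negative only at the first swab after discharge. With equal underlying clearance it reached about 1.09.

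**6. Against sampling error.** With equal arms and d clearance events, SE(log HR) ≈ 2/√d. For d = 36 (SAP 6.1.5.1 uses 36 infections as a possible lock trigger), exp(1.96 × 2/6) = 1.92. For d = 100 (assumed), exp(1.96 × 0.2) = 1.48. The 95% interval then runs a factor of about 1.5 to 1.9 either side of the estimate.

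**The case against.** The case for leaving the rule alone has five parts.

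**Swabs resume after discharge, and the early termination visit has one.** This stands. A reader might infer that everyone admitted stays in the risk set untested to Day 57, which would put the shift near the top of the range in step 4. The schedule footnotes do not support that: it would need stays that outlast the Evaluation Period or withdrawal while in hospital. The figures with no one re-swabbed are an outer bound.

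**The plan's risk ratio of 0.33 does not give the hospitalised shares.** This stands. A reader might carry it over, but Protocol 9.2 assumes it for the primary and key secondary endpoints, which do not include hospitalisation. It also refers to incidence among all Prevention participants, whereas this analysis includes only the infected. If infection and moderate-or-worse disease both fall by 0.33, the share of infected participants with worse disease is unchanged (0.33/0.33 = 1, setting aside the 4- and 8-week windows). A lower hospitalised share on active drug is possible, but the plan does not state it.

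**Remote visits are not shown to lack swabs.** This stands. Protocol 1.3 allows remote assessments for positive participants, and a reader might take this as a second waiver. It refers to the visit-type table, where home visits follow the schedule and only hospitalised participants have virtual visits.

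**Censoring at the last RT-PCR has its own bias.** This stands in part. If hospitalised participants clear more slowly, censoring near admission is informative. In a simulation with assumed medians of 24 vs 12 days, 20% vs 7% hospitalised and half never re-swabbed, full swabbing gave 1.10, the last-visit rule 1.20 and last-RT-PCR censoring 1.06. The proposed rule misses by 0.04 and the written rule by 0.10, in opposite directions.

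**The endpoint is exploratory and imprecise.** This stands and sets the severity. It carries no alpha and no sample-size role, the objective is to characterise, and step 6 shows sampling error well above a shift of 0 to 0.06.

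None of this makes an untested day an observation of non-clearance.

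**Conclusion.** The censoring rule is wrong for an endpoint that only a swab can reveal, and nothing else in the SAP corrects it. The effect is limited to participants who never test negative and whose last visit had no swab.

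In the placebo-controlled populations (Part 1 and Part 2 Prevention), the clearance hazard ratio is biased towards active drug if the hospitalised share of infected participants is lower there. The simulated size is about 0 to 0.06 when all stays end in discharge and about 0.03 to 0.16 when 30% of the hospitalised are never swabbed again. Both ranges rest on assumed shares, stays and clearance times. Equal shares give no bias.

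A reader might extend the direction to every population analysed. The protocol does not support this: Part 2 Treatment and Part 3 each randomise between two active arms (Protocol 6.3 and 9.3), so no direction can be stated. SAP Table PYAD.6.1 lists placebo under Part 2 Treatment, which conflicts with the protocol and needs reconciling separately.

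Severity is minor. Primary and key secondary conclusions do not depend on this analysis.

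**What to change.** In SAP 6.16.1.4, censor participants without a negative test at the date of their last RT-PCR result in the Evaluation Period.

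Add a sensitivity analysis that treats clearance as interval-censored between the last positive and the first negative swab, with right-censoring at the last swab for those never negative. This addresses late detection after missed in-hospital swabs, which the new censoring date does not remove.

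The cost is one sentence and one line of derivation code for the censoring date, plus one further model, all from dates already collected. The downsides are less nominal follow-up time, though the lost time holds no information on clearance, and possibly informative censoring near admission. The report should state the second and give, by arm, the number of participants whose last visit had no swab.

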#### 6.16.1.5. Viral Resistance

If appropriate, the evaluation of viral resistance will be conducted as described in a separate bioanalytical analysis plan for the Prevention and Treatment populations.

#### 6.16.1.6. Duration of Hospitalization

Treatment comparisons of the mean DOH (in days) due to COVID-19 will be compared between each study intervention and placebo using a nonparametric rank-sum test (such as Mann-Whitney or van Elteren test) adjusting for facility and for the randomization stratification factors. This comparison will be made on the Prevention and Treatment populations.

### 6.16.2. Additional Exploratory Analyses not Defined in the Protocol

In addition to the protocol defined endpoints, additional sensitivity analyses may be performed if deemed appropriate.

Additional analyses include:

#### 6.16.2.1. SARS-CoV-2 Viral Load over Time

For quantitative viral load endpoints in the trial, the Ct values will be utilized with the following considerations:

- Two Ct values will be provided on 2 different genes: N1 and N2. N1 will be used as the primary measure; N2 will only be used when the Ct value for N1 is not available.
- Ct values range between 0 and 45.
- Negative SARS-CoV-2 tests will be associated with a Ct value of 45.
- The (log base 10) viral load will be calculated from the Ct value  $(45-Ct)/\log_{10}$ , or  $(45-Ct)/3.321928$ .

For participants who are SARS-CoV-2 positive at baseline or at any time during the Evaluation Period, change from the date of confirmed infection to the end of the Evaluation Period of SARS-CoV-2 viral load data in the log base 10 scale will be statistically analyzed using a MMRM analysis method. The model will contain log base 10 transformed viral load at time of confirmed infection as a covariate, treatment, days since confirmed infection (day), treatment-by-day interaction, facility, and the randomization stratification factors as fixed effects.

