2.2. Background

The SARS-CoV-2 gains entry to cells through binding of the spike (S) protein to ACE2 receptors on cells (Hoffmann 2020). LY3819253 and LY3832479 are neutralizing immunoglobulin G1 (IgG1) monoclonal antibodies (mAb) to the spike protein of SARS-CoV-2. They are designed to block viral attachment and entry into human cells, and to neutralize the virus. The blocking of viral entry into respiratory cells and viral replication is expected to prevent and/or mitigate the severity of disease in people whom ongoing viral spread and replication is the primary driver of COVID-19 pathophysiology. For those that become infected, the decrease in viral replication may also shorten a patient's extent and duration of viral shedding and transmission, positively impacting public health.

Lilly is evaluating the safety, tolerability, pharmacokinetics (PK), and pharmacodynamics (PD) of LY3819253 in participants hospitalized for COVID-19, in Study J2W-MC-PYAA (PYAA), a randomized, placebo-controlled, double-blind, single ascending dose, Phase 1, first in human study.

Lilly is evaluating the safety, tolerability, PK, and immunogenicity of LY3832479 in healthy participants, in a randomized, placebo-controlled, single dose, Phase 1 study (Study J2Z-MC-PGAA [PGAA]) under IND 150707. Concurrent with Study PGAA, LY3832479 is also under development in China in an ongoing Phase 1 clinical study in healthy participants, Study JS016-001-I. Both studies have started prior to this amendment.

In addition, the impact of LY3819253, alone or in combination with LY3832479, on viral load and clinical outcomes in participants with early mild to moderate COVID-19 illness is being

investigated in Study J2W-MC-PYAB (PYAB), a Phase 2, randomized, double-blind study. Interim analysis from this study suggests treatment with LY3819253 may decrease the risk of hospitalization in patients with mild to moderate COVID-19 (Chen et al. 2020)

Additional information about these studies can be found in the Investigator's Brochure (IB).

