#### 6.1.1. Analysis Populations

Patient populations are defined in [Table PYAD.6.1](#) along with the analysis they will be used to conduct. The treatment groups and inferential comparisons described in [Table PYAD.6.1](#) will be used unless otherwise specified. Also, unless otherwise specified, for all populations/analysis, patients will be analyzed according to the treatment to which they were assigned.

If enrolling to a placebo-controlled trial is challenged by an effective medication becoming available for prevention of COVID-19 and SARS-CoV-2, then the placebo arm may be dropped in Part 2.

Throughout the document, the term “the Prevention populations” will be used to describe both the Part 1 Prevention and Part 2 Prevention populations. Analyses on the Prevention populations will be conducted on each Prevention population separately. The terms “the Treatment populations” and “the Safety populations” are defined similarly, including those populations from Part 3 of the study.

Table PYAD.6.1. Analysis Populations

Population	Description
Entered	
Definition: All patients who signed informed consent.
 
Purpose: Used for disposition analysis.
 
Treatment Groups: None
 
Inferential Comparisons: None

Enrolled/Intent-to-Treat (ITT)	
Definition: All participants assigned to treatment, regardless of whether they take any doses of study treatment, or if they took the correct treatment. Patients will be analyzed according to the treatment group to which they were assigned.
 
Purpose: Used for disposition, demographic, and safety analyses.
 
Treatment Groups (Short Label):
 
 
Part 1: 4200 mg LY3819253 (4200 LY) and placebo (Pbo)
 
Part 2: 700 mg LY3819253, 350 mg LY3819253 + 700mg LY3832479, and placebo
 
 
Inferential Comparisons: LY versus placebo

Part 1 Prevention	
Definition: All participants in the Enrolled/Intent-to-Treat population in Part 1 who are SARS-CoV-2 RT-PCR negative and serology negative at baseline.
 
Purpose: Used for efficacy and health outcomes analyses.
 
Treatment Groups (Short Label): 4200 mg LY3819253 (4200 LY) and placebo (Pbo)
 
Inferential Comparisons: LY versus placebo

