### **6.1.2. Definition of Study Baseline**

Unless otherwise specified, for all measurements, baseline is defined as the last nonmissing assessment recorded on, or prior to, the date of the study drug administration at study Day 1.

Baseline SARS-CoV-2 RT-PCR and serology status will be based on evaluable test results on, or prior to, the date of study drug administration at study Day 1. A participant will be considered RT-PCR positive at baseline if any RT-PCR result is determined to be positive.

Baseline for safety analysis is described in the safety section.

Change from baseline will be calculated as the visit value of interest minus the baseline value. If a baseline value or the value at the visit is missing for a particular variable, then the change from baseline is defined as missing.

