**Table PYAD.6.2. Definition of Study Period Time Intervals**

Study Period	Interval Start Definition	Interval End Definition
Screening: All patients who sign informed consent are considered as entering the Screening Period.	Informed consent date	Prior to the start of Evaluation Period.
Evaluation Period: All patients who are randomized to the study are considered as entering the Evaluation Period.	At the start of study drug administration date/time following randomization. For patients who are randomized but not dosed, the Evaluation Period starts on the date of randomization.	The minimum of Evaluation Period discontinued date, study discontinuation date, or first Follow-Up visit date.
Follow-Up: All patients who had a follow up visit are considered as entering follow-up period.	After the Evaluation Period ends.	The maximum of the last study visit date or study disposition date.

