## **6.2. Adjustments for Covariates**

Unless otherwise specified, efficacy analyses will adjust for the baseline value of the endpoint when modeling estimates and calculating p-values.

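### In Prevention participants the exploratory viral load model takes change from, and adjusts for, a value measured after dosing, so part of any antiviral effect may be adjusted away

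*SAP*

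**What the plan says.** SAP 6.16.2.1 is one of the additional exploratory analyses that the protocol does not define. It applies to the following set: "For participants who are SARS-CoV-2 positive at baseline or at any time during the Evaluation Period". The response is "change from the date of confirmed infection to the end of the Evaluation Period of SARS-CoV-2 viral load data", on the log10 scale, analysed by MMRM. On the covariate the section says: "The model will contain log base 10 transformed viral load at time of confirmed infection as a covariate". The other terms are treatment, day since confirmed infection, their interaction, facility and the stratification factors. A negative test is given a Ct of 45.

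Three other places in the SAP bear on this.

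- SAP 6.1.1 defines the Part 1 Prevention population as "All participants in the Enrolled/Intent-to-Treat population in Part 1 who are SARS-CoV-2 RT-PCR negative and serology negative at baseline". The Part 2 definition has the same two conditions within the Prevention Cohort.
- Table PYAD.6.2 starts the Evaluation Period thus: "At the start of study drug administration date/time following randomization". Participants randomized but not dosed start at randomization.
- SAP 6.1.2 says that, unless otherwise specified, "baseline is defined as the last nonmissing assessment recorded on, or prior to, the date of the study drug administration at study Day 1". SAP 6.2 says, with the same proviso, that "efficacy analyses will adjust for the baseline value of the endpoint when modeling estimates and calculating p-values".

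Protocol 2.2 describes antibodies meant to block viral entry and neutralize virus. In those who become infected, it says, "the decrease in viral replication may also shorten" the extent and duration of shedding.

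**The concern.** A covariate in a randomized comparison should be fixed before treatment can act on it. For participants positive at baseline, the load at confirmed infection is the pre-dose Day 1 value, and using it is sound. For Prevention participants it is measured days to weeks after the infusion. If the antibody has already lowered the load by then, subtracting that value and adjusting for it holds constant part of what the drug did.

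The set analysed is a second difficulty. Only participants infected after dosing contribute, and infection is what the drug is meant to prevent. Protocol 9.2 plans for a risk ratio of 0.33 on the primary and key secondary endpoints, which include infection within 4 weeks. On that assumption about three placebo participants enter for each active one of an equal-sized arm (1/0.33 = 3.0). The arms being compared are then no longer the randomized groups, and the resulting bias can go either way.

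At stake is how the quantitative virology in Prevention participants is read. A weak result could mean a weak drug effect on viral load, or it could be produced by the model.

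**Working it through.** The documents attach no sample size, power or effect size to this analysis, so there is no stated figure to reproduce. The check has two steps.

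**Step 1: when is the reference value measured?** Prevention participants are RT-PCR negative at baseline, and the Evaluation Period begins at dosing (or at randomization if not dosed). Their first positive therefore falls after that start. The SAP does not define confirmed infection, but any reading gives a post-dose date for these participants. The general baseline rule would give them a load of (45 - 45)/3.321928 = 0. That is the same for everyone, so no informative pre-dose load is available to replace the covariate.

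**Step 2: what does the model estimate?** Let Y0 be the log10 load at first detection, Y1 a later load and A the treatment.

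- Planned model: Y1 - Y0 = a + τA + βY0 + error.
- Moving Y0 across: Y1 = a + τA + (1 + β)Y0 + error. The treatment coefficient τ is unchanged, so the planned analysis is the same as modelling later load adjusted for first load.
- With total effects d0 on Y0 and d1 on Y1, equal SDs and within-arm correlation rho: **τ = d1 - rho × d0**.
- Share of the later-load effect kept: 1 - rho × d0/d1.

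The values of d0, d1 and rho are assumptions; none is in the documents. With d1 = -1.0 log10:

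| d0 (log10) | rho = 0.3 | rho = 0.5 | rho = 0.7 |
|---|---|---|---|
| 0 | -1.00 (100%) | -1.00 (100%) | -1.00 (100%) |
| -0.5 | -0.85 (85%) | -0.75 (75%) | -0.65 (65%) |
| -1.0 | -0.70 (70%) | -0.50 (50%) | -0.30 (30%) |

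A simulation of 200,000 participants per cell (SD 1.5 at both times) gave -0.99, -1.00 and -1.00 in the first row; -0.85, -0.75 and -0.65 in the second; and -0.70, -0.50 and -0.30 in the third. Comparing Y1 without Y0 recovered -0.99 to -1.01 throughout.

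A harsher case is a constant shift of 1.5 log10 at every swab, with between-person SD 1.2 and within-person SD 0.7. Then rho = 1.44/(1.44 + 0.49) = 1.44/1.93 = 0.746, and τ = -1.5 × (1 - 0.746) = -0.38. The model keeps 0.38/1.5 = 25%.

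A milder case is a simulated growth-and-decline curve with weekly swabs and a lag of 0 to 7 days to detection. It gave -1.37 against a true Day 7 difference of -1.48, so it keeps 1.37/1.48 = 93%.

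**The case against.** **The analysis is exploratory.** This stands. It is outside the testing scheme of SAP 6.5, and SAP 6.11 allows alternative approaches, including to the viral load definition. Still, it is the only model of quantitative viral load that the SAP specifies for Prevention participants. The clearance analyses use positive or negative results, and SAP 6.16.2.7 covers Part 3 only.

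**The protocol asks about infected participants.** Protocol section 3 sets out to characterize viral endpoints in those who become RT-PCR positive. The course after detection is a fair descriptive question, so the infected-only analysis should stay. What it cannot carry is a model-adjusted treatment effect read as a randomized comparison.

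**The loss may be small.** This also stands. With weekly swabs the first positive can fall anywhere on the curve, which weakens its link with later load; the milder case keeps 93%.

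A reader might also infer three stronger things.

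- *That baseline-positive and later-infected participants are pooled in one model, spoiling the Treatment estimate.* The section names no population. SAP 6.16.1.4 and 6.16.2.3 use similar inclusion wording and then report for the Prevention and Treatment populations, and SAP 6.1.1 analyses each Prevention population separately. This is an ambiguity, not a demonstrated pooling.
- *That a constant reduction in load would show no effect at all.* That is true of an unadjusted change score. The SAP includes the covariate, so part of the effect remains.
- *That the sign could reverse.* None of the cases above does so. The formula would need the later-load effect to be smaller than rho times the first-detection effect, and the documents give no ground for expecting that.

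**Conclusion.** The point holds in a limited form. For Prevention participants the reference value and covariate in SAP 6.16.2.1 are always post-dose, which departs without explanation from the SAP's general baseline and covariate rules. The provisos allow a departure, but they do not make the value a baseline. Whenever the antibody lowers load at first detection and the two loads are positively correlated, the model understates the effect on later load.

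Under the assumed inputs it keeps roughly 25% to 100%. There is no loss if load at first detection is unaffected, and the low end requires the full effect to be present already at first detection with a correlation near 0.75. These figures rest on equal variances and on values that the documents do not give. They also exclude any bias from analysing only those infected after dosing. For baseline-positive participants the covariate is valid.

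No primary or key secondary conclusion is affected. The change is still worth making, because it is nearly free and a weak virology result could not otherwise be interpreted.

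**What to change.** 1. **Separate the populations.** State that the model is run by population. Keep the change-from-baseline MMRM for the Treatment populations, with the pre-dose Day 1 load as covariate, matched to the swab type used later. In Part 1 that is the Day 1 nasal swab, with a note that its value can be 0 when only the nasopharyngeal swab was positive.
2. **Prevention participants who become infected.** Report log10 load at first detection by arm as an outcome. Model later load by day without the change score and without the post-dose covariate. Label the comparison descriptive, because the subset is formed after randomization.
3. **Optional addition.** At the End of Evaluation lock, compare peak log10 load in all Prevention participants by a rank test, with negatives set to 0 through the existing Ct 45 rule. State how swabs missed during hospitalization are handled, since the schedule does not require them there.

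The cost is SAP wording and a little programming. Item 2 gives up whatever precision the covariate would bring. Item 3 keeps the randomized groups, but most values would be 0, so it mixes infection incidence with viral load and partly repeats the Day 29 and Day 57 infection endpoints. It should be an addition, not a replacement.
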